# 9.0 ASSESSMENTS

### 9.1 Safety Assessments

Data on local and systemic solicited adverse events will be collected by structured interview, using specific questions. Data on other adverse events will

be collected with an open-ended question. All data will be recorded on the appropriate source documents.

The local and systemic solicited adverse events will be collected and the vital signs will be measured by study staff prior to vaccination and at least 30 minutes post-vaccination as specified in the Schedule of Procedures (Appendices A, B and C)

## 9.1.1 Local solicited adverse events

The presence of local solicited adverse events will be assessed at the time points specified in the Schedule of Procedures (Appendices A, B and C).

Local solicited adverse events (pain, tenderness, erythema/skin discoloration, induration, oedema) will be assessed and graded using the Appendix D, Adverse Event Severity Assessment Table as a guideline.

## 9.1.2 Systemic solicited adverse events

The presence of systemic solicited adverse events will be assessed at the time points specified in the Schedule of Procedures (Appendices A, B and C).

Fever, chills, headache, malaise, sweating, fatigue, myalgia, arthralgia, nausea, vomiting, diarrhoea and abdominal pain, will be assessed and graded using the Appendix D, Adverse Event Severity Assessment Table as a guideline.

## 9.1.3 Vital Signs

At the vaccination visits, vital signs (pulse, respiratory rate, blood pressure and temperature) will be measured by study staff prior to vaccination and at least 30 minutes post-vaccination.

For the other study visits vital signs will be assessed at the time points specified in the Schedule of Procedures (Appendices A, B and C).

## 9.1.4 Other adverse events

Occurrence of other adverse events, including autoimmune disease and connective tissue disorders (including Serious Adverse Events) will be collected following an open question to volunteers on the time points according to the Schedule of Procedures (Appendices A, B and C). The adverse events will be graded using the Appendix D, Adverse Event Severity Assessment Table as a guideline.

For more information regarding adverse events refer to Section 10.0, Adverse Events.

## 9.1.5 Concomitant Medications

During the study, information regarding concomitant medications and reasons for their use will be solicited from the study volunteers at each visit and recorded.

Concomitant receipt of Investigational Products, including other HIV vaccines is prohibited during the study.

If clinically indicated, non-live vaccines (non-HIV) and immunoglobulin may be given up to 14 days before study vaccination(s) or after postvaccination blood draw (i.e., 14 days or more after any study vaccinations).

Live-attenuated vaccines (non-HIV) may be given 60 days before study vaccination(s) or 60 days after the post-vaccination blood draw (live attenuated flu vaccine may be given within 14 days before study vaccination(s) or after the 14-day post-vaccination blood draw). However, the study vaccination(s) should not be given if there are any continuing symptoms from recently administered non-HIV vaccines. In this situation, the CRC investigator should consult with IAVI Medical Monitor before administering the next study vaccination.

If the use of a short tapering (<2 weeks) course of oral corticosteroids is required, the study vaccinations may be continued after a 4 week washout period provided that the medical condition requiring this therapy has resolved completely and in the opinion of both the CRC investigator and IAVI Medical Monitor the continuation of the study vaccinations will not jeopardize the safety of the volunteer. Volunteers requiring chronic (> 2 weeks) or long term therapy will not receive any further vaccinations but will continue with follow-up visits until the end of the study.

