- 10. Any of the following abnormal laboratory parameters listed below (laboratory parameters must be consistent with I/E criteria prior to each vaccination):
  - i. Hematology
    - a. Hemoglobin <10.0 g/dL
    - b. Absolute Neutrophil Count (ANC):  $\leq 1000/\text{mm}^3$
    - c. Absolute Lymphocyte Count (ALC):  $\leq$  500/mm^3
    - d. Platelets:  $\leq 90,000/$  mm^3
    - ii. Chemistry
      - a. Creatinine: > 1. 1 x ULN
      - b. AST: >1.25 x ULN
      - c. ALT: >1.25 x ULN
  - iii. Urinalysis: abnormal dipstick confirmed by microscopy
    - a. Protein 2+ or more
    - b. Blood 2+ or more (not due to menses)
    - c. Leukocytes 2+ or more
- 11. Receipt of live-attenuated vaccine within the previous 60 days (live attenuated flu vaccine within 14 days) or planned receipt within 60 days after vaccination with Investigational Product; or receipt of other vaccine (e.g. pneumococcal), allergy treatment with antigen injections or tuberculin skin test within the previous 14 days or planned receipt within 14 days after vaccination with Investigational Product
- 12. Receipt of blood transfusion or blood-derived products within the previous 6 months
- 13. Participation in another clinical trial of an Investigational Product currently, within the previous 3 months or expected participation during this study
- 14. Prior receipt of another investigational HIV vaccine candidate (note: receipt of an HIV vaccine placebo will not exclude a volunteer from participation if documentation is available and the IAVI Medical Monitor gives approval)
- 15. History of severe local or systemic reactogenicity to vaccines (e.g.

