# 12.0 DISCONTINUATION OF VACCINATIONS AND/OR WITHDRAWAL FROM STUDY

## 12.1 Discontinuation of Vaccinations

Any volunteer discontinuing from further vaccinations or being considered for discontinuation of vaccinations will be discussed with the sponsor. Volunteers will be discontinued from further vaccination for any of the following reasons:

- 1. Pregnancy
- 2. Intercurrent HIV Infection
- 3. Use of systemic corticosteroids, immunosuppressive, antiviral, anticancer, antituberculosis or other medications considered significant by the investigator
- 4. A disease or condition or an adverse event that may develop, regardless of relationship to the Investigational Product, if the principal investigator or designee is of the opinion that further study vaccinations will jeopardize the safety of the volunteer
- 5. Any of the following current abnormal laboratory parameters which are known at the time of vaccination:

Haematology

- Haemoglobin <9.0 g/dL or <1.40 mmol/L
- Absolute Neutrophil Count (ANC): < 1000/mm3 or < 1.0 x  $10^{9}$ /L
- Absolute Lymphocyte Count (ALC):  $\leq$  500/mm3 or  $\leq$  0.5 x 10^9/L
- Platelets:  $\leq 90,000 \geq 550,000/\text{mm3} \text{ or } \leq 90 \times 10^9 \geq 550 \times 10^9/\text{L}$

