## Chemistry

- Creatinine: >1.4 x ULN
- AST: >3.0 x ULN
- ALT: >3.0 x ULN

Urinalysis: Dipstick 3+ confirmed by microscopy for

- Protein
- Blood (not due to menses)
- Leukocytes
- 6. Receipt of live attenuated vaccine within the previous 60 days (live attenuated flu vaccine within 14 days) or planned receipt within 60 days after vaccination with Investigational Product or receipt of other vaccine within the previous 14 days or planned receipt within 14 days after vaccination with Investigational Product
- 7. A Grade 4 local reactogenicity event (as per Appendix D) involving the injected arm
- 8. Anaphylaxis; bronchospasm; laryngeal oedema; convulsions or encephalopathy following study vaccinations.
- 9. Life threatening adverse event following study vaccinations unless not related to the Investigational Product and fully resolved.
- 10. Any immediate hypersensitivity reaction judged to be related to the Investigational Product, if the principal investigator or designee is of the opinion that further study vaccinations will jeopardize the safety of the volunteer
- 11. Volunteer requests to discontinue further vaccination.
- 12. Participating in another clinical study of an Investigational Product

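### Section 9.1.5 permits live attenuated flu vaccine in the 14 days before a study dose, the window in which 12.1 item 6 requires vaccination to stop; its 14-day blood draw is scheduled after only 2 of 12 group-by-dose vaccinations

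*Protocol*

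**What the plan says.** **Section 9.1.5 (Concomitant Medications)** sets the rule for live flu vaccine: "live attenuated flu vaccine may be given within 14 days before study vaccination(s) or after the 14-day post-vaccination blood draw". It adds that "the study vaccination(s) should not be given if there are any continuing symptoms from recently administered non-HIV vaccines". For non-live vaccines and immunoglobulin, release after a dose is "after postvaccination blood draw (i.e., 14 days or more after any study vaccinations". For other live vaccines it is "60 days after the post-vaccination blood draw".

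**Section 12.1 (Discontinuation of Vaccinations)** opens its list with "Volunteers will be discontinued from further vaccination for any of the following reasons". Item 6 of the list includes "Receipt of live attenuated vaccine within the previous 60 days (live attenuated flu vaccine within 14 days", and a second limb covers "planned receipt within 60 days after vaccination with Investigational Product".

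**Section 5.2.4, exclusion criterion 11**, applies the same pre-dose bar at entry: "Receipt of live-attenuated vaccine within the previous 60 days (live attenuated flu vaccine within 14 days".

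**Section 6.3 and Appendices A to C** place a visit 14 days (plus or minus 3) after every dose. Specimens are taken at that visit only where the schedule marks them.

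**The concern.** Two sections forbid the window that a third permits. Section 9.1.5 is where a centre would look when a volunteer asks about a flu vaccine between doses, and 12.1 decides whether the next dose is given. A volunteer who is told that live flu vaccine is allowed the week before dose 2 then meets a listed reason for discontinuation when dose 2 falls due. No other text in the protocol reconciles the two. These are operative dosing rules, which a statistical analysis plan would not settle.

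The release point after a dose is a lesser matter. It is tied to a 14-day blood draw that most doses do not have, so the sentence gives a centre no event to wait for.

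At stake is an avoidable loss of doses in a trial with 28 vaccine recipients per group, and inconsistent handling between centres.

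**Working it through.** The plan gives no figure of its own on this point, so there is none to reproduce. All days below are nominal.

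**1. The rules side by side (live flu vaccine before a dose)**

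| Section | Last 14 days before a dose |
|---|---|
| 9.1.5 | permitted |
| 12.1 item 6 | reason to discontinue |
| 5.2.4 criterion 11 | excluded at entry |

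Elsewhere in the same paragraph of 9.1.5, the rule for other live vaccines reads as a minimum gap of 60 days. Only the flu clause uses a word that means inside the interval. The intent was probably the opposite, but the text as it stands permits what 12.1 forbids.

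**2. Days affected**

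Inputs: dose days from Appendices A to C are 0, 28, 112 (Groups A, B, D) and 0, 84, 112 (Group C). Each group has one 28-day and one 84-day interval.

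- Days open under 9.1.5, from day 14 after a dose to the day before the next dose: 28 − 14 = 14 and 84 − 14 = 70, so 84 in every group.
- Open days fewer than 14 days before the next dose: D15–D27 and D99–D111 in A, B and D; D71–D83 and D99–D111 in C. That is 13 + 13 = 26.
- Share: 26/84 = 31%. In the 28-day interval it is 13 of 14.
- If the day exactly 14 days before a dose also counts as inside the bar, the figures are 14 + 14 = 28 of 84 (33%), and 14 of 14 in the 28-day interval.

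**3. Expected number of volunteers**

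- Exposure: 140 × 26 = 3640 volunteer-days; 3640/365.25 = 9.97 person-years.
- Assumption, not in the protocol: 0.5% to 5% of volunteers a year receive live flu vaccine.
- Expected stops: 9.97 × 0.005 = 0.05, and 9.97 × 0.05 = 0.50.

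**4. Blood marked 14 days after a dose**

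| Group | Dose 1 | Dose 2 | Dose 3 |
|---|---|---|---|
| A | D14 none | D42 ICS | D126 none |
| B | D14 none | D42 ICS | D126 none |
| C | D14 none | D98 none | D126 none |
| D | D14 none | D42 none | D126 none |

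Four groups × three doses = 12 vaccinations, of which 2 have a blood sample at day 14. Urinalysis is marked at all 12 visits. Haematology and chemistry are drawn one week after each dose.

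**The case against.** The strongest reply is that this is one misworded parenthesis whose intent is clear, and that 12.1 requires any volunteer considered for discontinuation to be discussed with the sponsor, so a centre would be corrected in time. That lowers the expected harm. It does not remove the contradiction, because by then the flu vaccine has been given and 12.1 leaves no discretion on its face.

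A reader might infer from the sentence on continuing symptoms that 9.1.5 positively expects every symptom-free recent recipient to be dosed. That goes too far: the sentence adds a condition and does not say it is the only one.

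On the blood draw, the sentence on non-live vaccines explains the draw as 14 days or more after a dose, and a centre could carry that over to flu vaccine. The anchor is also correct where it matters most. The D42 ICS sample in Groups A and B is the primary immunogenicity time point, and its window runs to D45. Waiting for the draw keeps another vaccine from being given on day 14, ahead of a sample taken on days 15 to 17. This objection stands: removing every blood-draw anchor would lose a useful protection.

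A reader might also infer a conflict for other live vaccines after dose 3. Counting 60 days from the dose gives 112 + 60 = D172. Counting from D119 blood, an unscheduled D126 draw or D140 blood gives D179, D186 or D200, which is 7 to 28 days later. The documents do not support calling this a conflict. Section 9.1.5 is the later date on every reading, so obeying it also satisfies the 60 days in 12.1. Section 12.1 governs further vaccination, and there is none after dose 3.

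**Conclusion.** The pre-dose contradiction for live flu vaccine holds and is minor. It rests on the plain wording of 9.1.5, 12.1 item 6 and exclusion 11, with no assumption needed. About a third of the days open between dose 1 and dose 3 lie in the stop window, as does nearly all of the open time in the 28-day interval. The expected number of volunteers stopped is at most about 0.5 of 140, and that figure depends on an assumed uptake that the protocol does not give.

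The 2-of-12 count is exact, but it is a secondary defect of labelling. It does not put the primary D42 comparison at risk.

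A related gap bears on the repair. The flu exception in 12.1 item 6 and exclusion 11 is attached only to past receipt. Read literally, the 60-day limb on planned receipt after a dose covers live flu vaccine too, whereas 9.1.5 releases it after about 14 days. Correcting 9.1.5 alone would leave that open.

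**What to change.** Make three small edits:

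1. In 9.1.5, for live attenuated flu vaccine, require more than 14 days before a study dose. A minimum of exactly 14 days would leave day 14 arguably inside the bar in 12.1.
2. In the same sentence, release live flu vaccine at 14 days or more after the dose and, after dose 2 in Groups A and B, not before the D42 ICS sample has been drawn.
3. In the planned-receipt limb of 12.1 item 6 and of exclusion 11, repeat the 14-day exception for live flu vaccine. Wording it as fewer than 14 days after the dose keeps day 14 from falling on both sides.

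Leave the anchors for non-live and other live vaccines as they are.

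**Cost.** No dose, visit or sample changes. Live flu vaccine keeps 84 − 28 = 56 of its 84 nominal open days (D42–D97 in A, B and D; D14–D69 in C), and none in the 28-day interval. If the D42 sample is taken as late as D45, Groups A and B keep 53. A volunteer who would have had the vaccine 14 days before a dose waits 28 days (D14 to D42, or D98 to D126), and up to 31 days around dose 2 in Groups A and B.

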# 9.1.6 Routine laboratory parameters

Table 3 shows the laboratory parameters that will be measured routinely. These will include haematology, clinical chemistry, immunological assays and urinalysis. The samples for these tests will be collected at the time points indicated in the Schedule of Procedures (Appendices A, B and C).

Laboratory Parameter	Test
Haematology	Full blood count (haemoglobin, haematocrit, erythrocytes, leucocytes, platelets).
	Differential count, absolute neutrophil count, absolute lymphocyte count
Clinical Chemistry	Liver function tests: aspartate transferase (AST), alanine transferase
	(ALT), total and direct bilirubin.
	Kidney function: creatinine

Table 3 Laboratory Parameters

Immunology	CD4+ and CD8+ T cells (absolute count)
Urinalysis	Dipstick test for protein, blood glucose, ketones, esterase
	(leukocytes), nitrite. If abnormalities (blood, protein, leucocytes) are found on dipstick test then further test will be performed (e.g., microscopy, culture)

## 9.1.7 Specific screening tests:

Volunteers will be screened to exclude the following diseases:

- Hepatitis B: positive for hepatitis B surface antigen (HBsAg)
- Hepatitis C: positive for hepatitis C antibodies (HCV antibodies)
- Syphilis: confirmed diagnosis of active syphilis (RPR and TPHA or equivalent)
- Tuberculosis: In volunteers presenting with productive cough of more than 15 days duration, a chest x-ray and sputum examination for Acid Fast Bacilli will be performed to rule out active tuberculosis

Volunteers will also be screened and excluded for the following:

• Seropositivity for Ad35-specific neutralizing antibody

## 9.2 Immunogenicity Assessments

## 9.2.1 Antibody Responses

Antibodies against vaccine encoded HIV proteins will be measured according to time points indicated on the Schedule of Procedures (Appendices A, B and C). Further antibody testing such as avidity or other functional antibody assays will be conducted if warranted.

Samples for neutralizing antibodies against the Ad35 vector will be taken at time points as indicated in the Schedule of Procedures (Appendices A, B and C).

## 9.2.2 Cellular Responses

Assays will be performed according to the IAVI Human Immunology laboratory and GSK SOPs as specified in the LAP Standard reagents will be used.

Immunogenicity assays, including ELISPOT and intracellular cytokine staining (ICS) assays for monitoring the number of circulating T cells that can be stimulated to produce cytokines, will be performed at time points indicated in the Schedule of Procedure (Appendices A, B and C), using peptide pools and/or proteins representing all or a portion of the vaccine encoded (GRIN and F4Co) antigen(s). Where feasible, ELISPOT assays will be performed on site using fresh or cryopreserved PBMC.

Pending the results of the secondary immunogenicity assays (ELISPOT and ICS), further exploratory studies may be carried out to look at the

breadth of the response via epitope mapping using vaccine matched peptides and cross-reactive epitopes using peptides from different HIVsubtypes. Vaccine induced T cell responses may be further characterized for HLA restriction and additional markers on the responding cells, such as markers for memory, activation, function or markers for homing to mucosal tissues. The ability of PBMC to restrict the growth of HIV in vitro may be examined using a Virus Inhibition Assay. The analytical plan for the immunology studies will be developed between IAVI, GSK and the CRC teams and an algorithm will be applied to determine which samples and time points are prioritized for exploratory assays.

## 9.2.3 PBMC, Serum and Plasma Storage

Samples of cryopreserved PBMC, plasma and serum will be taken at time points as indicated in the Schedule of Procedures (Appendices A, B and C) for purposes of standardisation, quality control and for future assays related to HIV vaccine research and development. These samples will be archived and only the volunteer identification number will identify the samples.

For the immunogenicity assessments, the laboratory personnel will be trained as necessary by the sponsor and provided with a written procedure manual. The sponsor will also provide specific instructions on reagents.

The samples described in 9.2.2 and 9.2.3 will be shipped routinely from each CRC to the IAVI Human Immunology Laboratory and the GSK laboratory as indicated in the Schedule of Procedures (Appendices A, B and C). The immunological testing will be performed at the CRCs, IAVI Human Immunology Laboratory and the GSK laboratory in accordance with organization standard SOPs and standard reagents.

## 9.3 Other Assessments

## 9.3.1 HLA (Human Leukocyte Antigen) Typing

Samples for HLA typing will be collected at the single time point indicated in the Schedule of Procedures (Appendices A, B and C).

HLA typing will be performed on samples that are selected for epitope mapping, VIA assays or other assay where the HLA type will inform the testing or interpretation of results.

## 9.3.2 HIV test

Samples will be tested at the time points indicated in the Schedule of Procedures (Appendices A, B and C). Further information is specified in Section 11.1 HIV Testing.

# 9.3.3 Pregnancy Test

A urine pregnancy test for all female volunteers will be performed by measurement of Human Chorionic Gonadotrophin ( $\beta$ hCG) at the time points indicated in the Schedule of Procedures (Appendices A, B and C).

The results of the pregnancy test must be negative prior to vaccination.

## 9.3.4 Ophthalmic Examination

The eye examination will be performed prior to the first vaccination and within one month of the final study visit in 100% of the volunteers enrolled in 2 centres (approximately 50% of enrolled volunteers). The purpose of this is to assess the effects of the investigational vaccine on structures and tissues of the eye, including lens opacities. The eye examination will be performed according to procedures detailed in the SOM.

# 10.0 ADVERSE EVENTS

## 10.1 Definition

An adverse event (AE) is any untoward medical occurrence in a volunteer administered Investigational Product and which does not necessarily have a causal relationship with the Investigational Product. An AE can therefore be any unfavourable or unintended sign (including an abnormal laboratory finding), symptom, or disease, temporally associated with the use of the Investigational Product whether or not related to the Investigational Product.

## 10.2 Assessment of Severity of Adverse Events

Assessment of severity of all AEs is ultimately the responsibility of the principal investigator.

The following general criteria should be used in assessing adverse events as Grade 1, 2, 3, or 4 if not identified elsewhere in the Adverse Event Severity Assessment Table (Appendix D).

- Grade 1: Symptoms causing no or minimal interference with usual social & functional activities;
- Grade 2: Symptoms causing greater than minimal interference with usual social & functional activities;
- Grade 3: Symptoms causing inability to perform usual social & functional activities;
- Grade 4: Symptoms causing inability to perform basic self-care functions OR Medical or operative intervention indicated to prevent permanent impairment, persistent disability, or death

Guidelines for assessing the severity of specific adverse events and laboratory abnormalities are listed in Appendix D, Adverse Event Severity Assessment Table.

## 10.3 Relationship to Investigational Product

The relationship of an (S)AE is assessed and determined by the Principal Investigator or designee. All medically indicated and available diagnostic methods (e.g., lab, blood smear, culture, X-ray, etc.) should be used to assess the nature and cause of the AE/SAE. Best clinical and scientific judgment should be used to assess relationship of AE/SAEs to the Investigational Product and/or other cause.

The following should be considered for the assessment of relationship of adverse events to the investigational Product:

- Presence/absence of a clear temporal (time) sequence between administration of the Investigational Product and the onset of AE/SAE
- Presence/absence of another cause that could more likely explain the AE/SAE (concurrent disease, concomitant medication, environmental or toxic factors, etc.)
- Whether or not the AE/SAE follows a known response pattern associated with the investigational Product

The relationship assessment should be reported as one of the following:

**Not Related**: clearly explained by another cause (concurrent disease, concomitant medication, environmental or toxic factors, etc.).

**Unlikely**: more likely explained by another cause (concurrent disease, concomitant medication, environmental or toxic factors, etc.).

**Possibly**: equally likely explained by another cause but the possibility of the Investigational Product relationship cannot be ruled out (e.g., reasonably well temporally related and/or follows a known Investigational Product response pattern but equally well explained by another cause).

**Probably**: more likely explained by the Investigational Product (e.g., reasonably well temporally related and/or follows a known Investigational Product response pattern and less likely explained by another cause).

**Definitely**: clearly related and most likely explained by the Investigational Product

For the purpose of expedited safety reporting, all possibly, probably or definitely related SAEs are considered Investigational Product related SAEs.

